## 7.9 Pharmacokinetic Analysis

Plasma concentrations of TAK-831 will be listed for each subject and summarized by each time point for each dose and period of the study.

Individual concentration-time data will be pooled to describe the population PK of TAK-831. As data permit, a nonlinear mixed effects modeling approach (NONMEM software) will be used to assess TAK-831 exposure. PK information generated in this study will be further utilized in subsequent population PK-PD analyses. The relationships between TAK-831 plasma concentrations and drug response will be explored. As appropriate, historical data may be used in

this analysis to increase the robustness of the model and precision of estimated parameters. Details of the modeling approach will be provided in a separate analysis plan, and the results of these analyses may be reported separately.

#### 7.10 Other Outcomes

Not applicable.

#### 7.11 Safety Analysis

The Safety Set will be used for all summaries of safety parameters. These summaries will be presented by placebo, each TAK-831 dose level, and TAK-831 overall (as appropriate).

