11.0 STATISTICAL METHODS

11.1 Statistical and Analytical Plans

A statistical analysis plan (SAP) will be prepared and finalized prior to unblinding of treatment assignments to the study team. This document will provide further details regarding the definition of analysis variables and analysis methodology to address all study objectives. In cases of inconsistencies between the protocol and the SAP in regard to data analysis, the SAP is to take precedence over the protocol. Due to this clear understanding of precedence, the statistical analysis section will not necessarily be updated to match the SAP when the protocol is amended.

A targeted data review will be conducted prior to unblinding of treatment assignments to the study team. This review will assess the accuracy and completeness of the study database, subject evaluability, and appropriateness of the planned statistical methods.

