11.1.5 Safety Analysis

The Safety Set will be used for all summaries of safety parameters. These summaries will be presented by cohort for placebo, each TAK-831 dose level, and TAK-831 overall (as appropriate).

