# 6.0 DETERMINATION OF SAMPLE SIZE

Up to approximately 32 subjects will be enrolled into this 2-period crossover study. Initially 16 subjects will be randomized to 1 of 2 sequences comparing the high dose to placebo. Based on the results of an interim analysis, an additional 16 subjects may be randomized as before or to 1 of the 2 sequences comparing the low dose to placebo.

The expected effect size, defined as the ratio between the mean difference between treatment and placebo divided by the standard deviation of this difference, is 0.6 for the primary endpoint. This effect size is a conservative estimate based on data from [1], which showed an effect size of 0.74 for EBC at 24 hours after initiation of treatment with secretin. In this study of a schizophrenic population, subjects on secretin showed a 24% higher rate of correct responses compared to subjects on placebo (70% vs 46%).

The sample sizes of 16 or 32 subjects have been selected to enable Bayesian analyses to inform dose selection and future drug development under the expected effect size as well as other plausible effect sizes.

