# 7.8 PD Analysis

# 7.8.1 Primary PD Endpoint

The primary endpoint is the average % of conditioned responses in the EBC task at Day 8.

The primary endpoint will be summarized for baseline, post-dose, and change from baseline by treatment.

Pairwise comparisons between active treatments and placebo will be generated within the framework of analysis of variance (ANOVA), with treatment sequence, period, and treatment as fixed effects. Subject nested within sequence is included as a random effect. The dependent variable is the change in response from the period baseline assessment to the final treatment day for each period, and the response data will be logit transformed before the change is calculated. The analysis will be performed using observed data. Potential carryover effects will be investigated. P-values and confidence intervals will be reported. The following SAS code may be used:

```
proc mixed data=XXXX;
class sequence treatment period subject;
model response = sequence treatment period / ddfm=kr;
random subject (sequence);
estimate 'Treatment Difference' treatment -1 1 / al alpha = 0.10 E;
lsmeans treatment;
run;
```

The primary endpoint will be tested individually for each of the two doses against 5% (one-sided) level of significance.

As a supplementary analysis, an ANCOVA (analysis of covariance) model will be applied to the primary endpoint with (period) baseline as a covariate, treatment sequence, period, treatment effect, baseline-by-treatment as fixed effects, and subject as a random effect. The dependent variable is the change in response from the period baseline assessment to the final treatment day for each period, and the response data will be logit transformed before the change is calculated. Based on a missing at random assumption, this analysis will be performed using observed data only. P-values and confidence intervals for this model will be provided.

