# 7.13 Changes in the Statistical Analysis Plan

The primary endpoint will be tested individually for each of the two doses against 5% (one-sided) level of significance.

The summaries of safety parameters will be presented by placebo, each TAK-831 dose level, and TAK-831 overall (as appropriate), rather than by cohort as stated in the protocol.

To increase statistical efficiency, baseline will be used as a covariate in the Bayesian normal linear model described in Section 7.8.1.

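### If the interim switches enrolment to 50 mg, the SAP's safety tables set each dose beside a placebo column about half of which comes from subjects never assigned that dose

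*SAP*

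**What the plan says.** Protocol 11.1.5 plans the safety tables with a cohort split: "These summaries will be presented by cohort for placebo, each TAK-831 dose level, and TAK-831 overall". SAP 7.11 omits the split: "These summaries will be presented by placebo, each TAK-831 dose level, and TAK-831 overall (as appropriate". SAP 7.13 declares the change, "rather than by cohort as stated in the protocol", without a reason. Where the two documents differ on analysis, Protocol 11.1 provides that "the SAP is to take precedence over the protocol", so the SAP layout governs.

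The subsections of SAP 7.11 on adverse events, laboratory values, vital signs, ECG and C-SSRS all summarise by treatment. SAP 7.1 does separate the dose levels if the low dose is used, but only for summaries by treatment sequence, which these are not.

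On who receives which dose, SAP 6.0 says: "Initially 16 subjects will be randomized to 1 of 2 sequences comparing the high dose to placebo". After the interim, "an additional 16 subjects may be randomized as before or to 1 of the 2 sequences comparing the low dose to placebo". Under SAP 7.12 the switch to 50 mg follows from success, from futility, or from the safety or tolerability of the high dose. Otherwise enrolment at 500 mg continues. Protocol 11.2 also allows enrolment to stop.

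**The concern.** In a two-period crossover, each dose has its own placebo data: the same subjects in their other period. Protocol 4.3 and 6.2.1 give this as the reason for the design. After a switch there are two such groups, formed one after the other. Randomisation decides the order of treatments within a group, but time of enrolment decides the dose.

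The groups may differ in background event rate. Up to two sites are allowed, and Amendment 06 raised the upper age limit from 50 to 60. The documents do not say when either took effect relative to the interim, so a difference is possible but not shown.

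The safety endpoints in SAP 5.1.4 are percentages of subjects, and no model adjusts them. The choice of columns is therefore the whole comparison. With one placebo column, a difference between groups can make one dose look worse and the other look better than against its own placebo.

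**Working it through.** **Inputs.** Group sizes of 16 and 16 are from SAP 6.0. The documents give no event rates or dropout rate, so those below are assumptions.

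**Step 1: the plan's figure.** 16 + 16 = 32, which matches the stated maximum of approximately 32.

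**Step 2: share of placebo subjects never assigned 500 mg.** Each completing subject contributes one placebo period. With n1 subjects in the 500 mg group and n2 in the 50 mg group, the share is n2/(n1 + n2).

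| Case | n1 | n2 | Share |
|---|---|---|---|
| Switch, as planned | 16 | 16 | 16/32 = 50% |
| Switch, uneven | 18 | 14 | 14/32 = 44% |
| Switch, uneven | 16 | 14 | 14/30 = 47% |
| Switch, uneven | 14 | 16 | 16/30 = 53% |
| Switch, uneven | 14 | 18 | 18/32 = 56% |
| Continue at 500 mg | 32 | 0 | 0% |
| No further enrolment | 16 | 0 | 0% |

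For the 50 mg column the share is n1/(n1 + n2), which spans the same range.

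Dropout changes this little. Assume that 10% or 20% leave before Period 2 and are not replaced. The share of placebo subjects who never took 500 mg is then 53% or 56% after a switch. If enrolment continues it is 5% or 11%, made up of placebo-first subjects who left early.

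**Step 3: effect on the displayed difference.** Let p1 and p2 be the placebo rates in the 500 mg and 50 mg groups. With equal groups, pooled placebo = (p1 + p2)/2. Displayed minus own-placebo difference is then:

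- 500 mg: p1 - (p1 + p2)/2 = (p1 - p2)/2
- 50 mg: p2 - (p1 + p2)/2 = (p2 - p1)/2

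The shifts are equal and opposite. Assumed values:

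| p1 | p2 | Pooled | Shift, 500 mg | Shift, 50 mg |
|---|---|---|---|---|
| 20% | 10% | 15% | +5 points | -5 points |
| 10% | 20% | 15% | -5 points | +5 points |
| 30% | 10% | 20% | +10 points | -10 points |
| 20% | 20% | 20% | 0 | 0 |

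In counts, as a hypothetical: 4/16 (25%) on 500 mg, 1/16 (6.25%) on the same subjects' placebo and 5/16 (31.25%) on the other group's placebo. Pooled placebo is 6/32 = 18.75%. The observed excess is 25 - 6.25 = 18.75 points against own placebo, but 25 - 18.75 = 6.25 points against the pooled column.

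**Step 4: what stays matched.** TAK-831 overall against pooled placebo compares the same 32 subjects with themselves and is not shifted.

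**Step 5: precision.** Take equal variances, equal group means and within-subject correlation ρ. The variance of the dose-placebo difference is proportional to 2 - 2ρ with own placebo and to 1.5 - ρ with pooled placebo. These are equal at ρ = 0.5. Below that value pooling is more precise; above it the dose's own placebo is.

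**The case against.** The strongest reply is that this is a declared choice of descriptive display. No safety test is planned (SAP 7.11.2 excludes inference for laboratory data unless otherwise stated), and no decision rule uses these columns. Laboratory and vital-sign listings carry treatment sequence, all adverse events are listed, and baseline characteristics are summarised by sequence with dose separated, so imbalance in those variables would be visible. This limits the consequence. It does not remove it, because listings do not give event rates by group.

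Pooling also has a merit. If the groups are alike and ρ is below 0.5, the pooled column is the more precise comparator. A gap of 1/16 against 5/16 has a two-sided Fisher p of about 0.17, so it could be chance. This stands, and is a reason to keep the pooled column.

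The SAP does not literally state a single pooled column, and its rider about appropriateness leaves some room. But 7.13 expressly sets the cohort split aside, so pooling remains the natural reading. It is fair to add that the protocol does not define cohort.

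A reader might infer more than the documents support:

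- **That half the placebo column is always unmatched.** It is so only after a switch; SAP 6.0 and 7.12 both allow enrolment to continue at 500 mg.
- **That the tables lose a paired analysis.** Percentages by treatment are marginal in either layout. What is lost is that the same subjects stand in both columns.
- **That the PD results are biased in the same way.** SAP 7.8.1 has a descriptive sentence, "The primary endpoint will be summarized for baseline, post-dose, and change from baseline by" treatment, but Protocol 11.1.4 never promised PD summaries by cohort. The primary ANOVA has sequence and subject-within-sequence terms.

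**Conclusion.** The point holds for one branch of the design. After a switch to 50 mg, about half of the placebo column beside each dose (16 of 32; 44% to 56% for the uneven splits examined) comes from subjects never assigned that dose. With equal groups, each displayed dose-placebo difference moves by half the gap between the groups' placebo rates. The size of that gap is unknown: the documents give no rates and do not show that the groups differ, and with equal rates the shift is zero. The conclusion assumes that placebo in SAP 7.11 means one column, which is the natural reading. If enrolment continues at 500 mg or stops, the by-cohort and by-treatment layouts coincide, apart from early dropouts. This is a worthwhile, inexpensive improvement to descriptive safety reporting. It does not challenge the PD model analyses.

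**What to change.** In SAP 7.11, add that when the low dose is used the safety tables show, in order: TAK-831 500 mg and placebo for the 500 mg group; TAK-831 50 mg and placebo for the 50 mg group; pooled placebo; TAK-831 overall. Define each group by the pair of sequences to which its subjects were randomised. Amend the 7.13 sentence on safety summaries to match. The same columns may be added to the descriptive by-treatment PD summaries in 7.8; the PD models need no change.

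The cost is two extra placebo columns and no new data. Each of those columns has only about 16 subjects and is noisier than the pooled one, which is why the pooled column should stay beside them.

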#### 7.11.1 Adverse Events

Verbatim terms will be coded by SOC and PT using MedDRA (version 20.0 or later).

TEAEs will be defined as any sign, symptom, syndrome, or new illness, regardless of relationship to study drug, that occur after the first dose of study drugs. TEAEs with onset occurring within 30 days (onset date – last date of dose  $+1 \le 30$ ) after study drug administration will be included in the summary tables. All AEs will be included in the listings.

TEAEs will be summarized by treatment. TEAE will only be included for the treatment administered in the Period of its start date, unless it increases in intensity in the following Period, in which case will be handled as a new TEAE on the second treatment.

When calculating the frequency and percentage of subjects who reported TEAEs, a subject will be counted only once for each SOC or PT when multiple TEAEs are coded to the same SOC or PT. For the intensity or relatedness summaries, if a subject reports multiple TEAEs coded to the same SOC or PT, the TEAE with maximum intensity or strongest relationship will be included in the summary. An exception to the previous rule is if the TEAE begins in Period 1 but increases in intensity in Period 2, in which case it will be summarized as separate TEAEs.

AEs with missing intensity will be listed as such in the AE listings, however, will be summarized as severe in summary tables. If the relationship of an event is missing, the relationship for the event will be considered to have been related.

In general, AEs will be tabulated at the following levels: overall summary (subjects with at least 1 AE in any dose or regimen), the MedDRA SOC, and the MedDRA PT. The tables will include the number and percentage (N[%]) of subjects. Summary tables that will be generated will include, but may not be limited to:

- Overview of Treatment-Emergent Adverse Events.
- Treatment-Emergent Adverse Events by System Organ Class and Preferred Term, including number of subjects and events.
- Treatment-Emergent Adverse Events by Preferred Term.

- Serious Treatment-Emergent Adverse Events by System Organ Class and Preferred Term, including number of subjects and events.
- Relationship of Treatment-Emergent Adverse Events to Study Drug by System Organ Class and Preferred Term.
- Drug-Related Treatment-Emergent Adverse Events by System Organ Class and Preferred Term
- Drug-Related Treatment-Emergent Adverse Events by Preferred Term.
- Intensity of Treatment-Emergent Adverse Events by System Organ Class and Preferred Term.
- Pretreatment Adverse Events by System Organ Class and Preferred Term.
- Most Frequent (>5%) Non-Serious Adverse Events by System Organ Class and Preferred Term
- Treatment-Emergent Adverse Events Leading to Study Drug Discontinuation by System Organ Class and Preferred Term.

In addition, subject mappings for the TEAEs by SOC and PT will be generated.

Data listings will be provided for pretreatment AEs, TEAEs, TEAEs leading to study drug discontinuation, liver function abnormalities, serious adverse events (SAEs), and AEs that resulted in death. AEs happened after 31 days post the last dose of the study drug will be listed as well.

## 7.11.2 Clinical Laboratory Evaluations

Clinical laboratory tests will be assessed using the Safety Set and will be evaluated and presented using International System of Units (SI) units unless otherwise stated. Refer to Protocol Section 9.2.17 as well as the schedule of the events for a list of all clinical laboratory tests.

All laboratory test parameters will be displayed in individual subject data listings. For test results not in SI units, the conversion to SI units will be done in the derived SDTM and ADaM datasets using the known conversion factors. If necessary, SI units from the central laboratory may be converted to Takeda's preferred SI units in the derived SDTM and ADaM datasets. All summaries and analyses will be based on the values using these preferred SI units.

Only observations within 3 days of the last dose of study drug will be included in the tables, with the exception of observations from the Early Termination Visit. No inferential statistics will be presented unless otherwise stated.

Descriptive statistics (N, mean, SD, median, minimum, and maximum) for the observed and change from baseline values will be presented by treatment. Baseline from each period will be used for change from baseline. Note that "character" urinalysis tests will only be listed.

Laboratory markedly abnormal values (MAVs), identified by the criteria defined in Appendix A, will be tabulated. If a subject has a MAV for a particular laboratory test, all visits for that subject

for that parameter will be listed. The number and percentage of subjects with at least 1 postdose markedly abnormal laboratory test result will be summarized by treatment. The mapping of the subjects who meet the MAV criteria will be listed as a table. All observations, including ones at unscheduled visits, will be included in the MAV evaluation and summaries.

Also, the elevated hepatic parameters will be summarized by treatment.

Listings of all clinical safety laboratory data will be provided in Appendix 16.2 Laboratory data outside of the normal reference range will be indicated in the listings. In addition, MAVs will be flagged. The listing will include site number, subject identifier, age, gender, treatment sequence, study period/visit, and sample collection date.

# 7.11.3 Vital Signs

Descriptive statistics (N, mean, SD, median, minimum, and maximum) will be used to summarize vital sign parameters at baseline, each post-baseline visit, and change from baseline to each post-baseline visit. Summaries will be by treatment. Baseline from each period will be used for change from baseline. Only observations within 3 days of the study drug will be included in the tables, with the exception of observations from the Early Termination Visit.

Vital sign MAVs, identified by the criteria defined in Appendix B, will be tabulated. If a subject has a MAV for a particular vital signs parameter, all visits for that subject for that parameter will be listed. The number and percentage of subjects with at least 1 postdose markedly abnormal vital signs measurement will be summarized by treatment. The mapping of the subjects who meet the MAV criteria will be listed as a table. All observations, including ones at unscheduled visits, will be included in the MAV evaluation and summaries.

Listings of all vital signs data will be provided in Appendix 16.2. Vital sign MAVs will be flagged in the listings. The listing will include site number, subject identifier, age, gender, treatment sequence, study period/visit, and sample collection date.

#### 7.11.4 12-Lead ECGs

Individual results of quantitative ECG parameters from the 12-lead safety ECGs that meet Takeda's markedly abnormal criteria will be summarized by treatment and provided in the data listings. Baseline from each period will be used for change from baseline. Baseline, postdose, and changes from Baseline in quantitative ECG parameters will be summarized. Shift tables will be generated to show the investigator's ECG interpretations at each postdose collection by the interpretation at Baseline.

All ECG data will be provided in the data listings.

# 7.11.5 Other Observations Related to Safety

Physical examination findings will be presented in the data listings. C-SSRS will be summarized by treatment.

#### 7.12 Interim Analysis

A planned unblinded interim analysis of the primary PD endpoints will be conducted when approximately 14 patients have been completed the primary endpoint. The site will be allowed to continue enrollment to the high/placebo comparison, with the goal that approximately 16 patients will be randomized by the time the interim analysis is complete. (The additional approximately 2 subjects will be included in the final analysis but not the interim analysis.) The interim PD analysis will be to determine whether to continue enrolling subjects to the high-dose/placebo comparison or switch enrollment to the low-dose/placebo comparison.

The Bayesian normal linear model described in Section 7.8.1 will be performed for the primary endpoint. "Success Stop criteria" at interim analysis is 70% posterior probability (or greater) of a difference between 500 mg TAK-831 and placebo >0.6 (on logit scale), and a decision of switching to the low dose will be made when "Success Stop criteria" are met. "Futility Stop criteria" will be met if the posterior probability of a difference between 500 mg TAK-831 and placebo >0.1 (on logit scale) is less than 30%, and a decision of switching to the low dose will be made. If none of the aforementioned criteria are met, a decision of continuing enrolling high-dose/placebo subjects ("Continue" decision) will be made.

In addition, a decision to switch to the low dose may be made based on the safety or tolerability of the high dose.

# 7.13 Changes in the Statistical Analysis Plan

The primary endpoint will be tested individually for each of the two doses against 5% (one-sided) level of significance.

The summaries of safety parameters will be presented by placebo, each TAK-831 dose level, and TAK-831 overall (as appropriate), rather than by cohort as stated in the protocol.

To increase statistical efficiency, baseline will be used as a covariate in the Bayesian normal linear model described in Section 7.8.1.

# Appendix A Criteria for Identification of Markedly Abnormal Laboratory Values Hematology—Criteria for Markedly Abnormal Values

Parameter	Unit	Low Abnormal	High Abnormal
Hemoglobin	Both	<0.8 × LLN	>1.2 × ULN
Hematocrit	Both	<0.8 × LLN	>1.2 × ULN
RBC count	Both	<0.8 × LLN	>1.2 × ULN
WBC count	Both	<0.5 x LLN	>1.5 x ULN
Platelet count	Conventional	$<75 \times 10^3/\mu L$	$>600 \times 10^{3}/\mu L$
	SI	<75 x 10  /L	$>600 \times 10^9/L$

LLN=lower limit of normal, RBC=red blood cell, ULN=upper limit of normal, WBC=white blood cell.

